8.1.1. Supplemental and Sensitivity Analyses

The primary analysis will be repeated in the Per Protocol analysis population, where subjects who were not compliant with the diary and/or treatment will be excluded from the analysis. The tabular and graphical summaries described in the previous section will be replicated for this Per Protocol analysis ([Table 16](#), [Figure 4](#), and [Figure 7](#)).

Sensitivity analyses will be performed using the stratified Cox proportional hazards model on both the mITT population and PP population using the worst-case scenario imputation method for subjects who drop out, are lost to follow-up, withdraw consent, or otherwise stop completing daily diary entries before clinical resolution ([Table 17](#)). These subjects will be censored at 180 days. Kaplan-Meier curves for each treatment arm will be presented ([Figure 5](#)). Kaplan-Meier curves for each treatment arm and duration of symptoms strata will be displayed in [Figure 8](#).

The primary analysis will be repeated on the mITT population using the subgroups defined in Section [6.4](#) ([Table 18](#)). A sensitivity analysis will be performed using the stratified Cox proportional hazards model on the mITT population with stratification based on subjects with less than 2 missing diaries per week versus

those with 2 or more missing diaries per week ([Table 19](#)). Kaplan-Meier curves for each treatment arm and diary compliance strata will be presented in [Figure 9](#).

8.2. Secondary Efficacy Analyses

The secondary efficacy outcome measures are as follows:

- The time from randomization to first negative viral load through 180 days.
- The change in viral titer between Day 1 and Day 180.

The protocol calls for a Log-Rank test to compare time from randomization to first negative viral load through 180 days between the nitazoxanide treated group and the placebo group; however, due to early closure of the study, the number of subjects is too small to use a Log-Rank test. Number and percentage of subjects with positive viral load and geometric mean viral titer in positive subjects with 95% confidence intervals will be presented by test type, treatment group and study day in the mITT Population ([Table 20](#)). A stratified Cox proportional hazards model will be used to compare treatment to control through Day 180 with respect to time to first negative viral load. Stratification will be based on acute versus chronic symptoms at baseline. GII and GI test types will be analyzed independently.

The analysis will be conducted in both the mITT population and the PP population. The treatment hazard ratio estimate, 95% confidence interval and p-value from the likelihood ratio test will be presented for each test type ([Table 21](#) and [Table 22](#)). The median time to clinical resolution and 95% confidence interval will be summarized by treatment arm and duration of symptoms for each test type. In addition, stratum-specific estimates of the treatment hazard ratio within each duration of symptoms strata will be presented for each test type. Kaplan-Meier curves for each treatment arm will be displayed in [Figure 10](#), [Figure 11](#), [Figure 12](#) and [Figure 13](#), for each test type in the mITT and PP populations. [Figure 14](#) and [Figure 15](#) will present Kaplan-Meier curves for each treatment arm and duration of symptoms strata for Norovirus GII and Norovirus GI test types, respectively, in the mITT population.

The analysis will be repeated on the mITT population using the subgroups defined in Section [6.4](#) for each test type ([Table 23](#) and [Table 24](#)).

The change in viral titer between Day 1 and Day 180 will be assessed using analysis of covariance (ANCOVA) adjusting for baseline viral titer. The analysis will be conducted in both the mITT population and the PP population for both Norovirus GII and Norovirus GI test types. [Table 25](#) and [Table 26](#) will present the observed means and standard deviations of the change in viral titer between Day 1 and Day 180 for each treatment group and duration of symptoms strata for Norovirus GII and Norovirus GI test types, respectively. Levene's test and normality checks will be carried out to check if the assumptions of ANCOVA are met. If assumptions of ANCOVA have been met, the adjusted mean, standard error, and 95% confidence intervals will also be presented for each treatment group and duration of symptoms strata. The p-value for the test of between treatment differences will also be presented. If the assumptions of ANCOVA are not met, transformations of the change in viral titer variable may be utilized to correct any skewness in residuals or heterogeneity of the variances. If a transformation of the dependent variable is used, a footnote in the table will denote which transformation was used in the analyses. If the assumptions of ANCOVA cannot be met through transformation of the dependent variable, only the observed mean, standard deviation and 95% confidence intervals of the unadjusted change in viral titer between Day 1 and Day 180 will be reported. A forest plot will display the adjusted means and 95% confidence intervals of the change in viral titer between Day 1 and Day 180 for each treatment group and duration of symptoms strata for each test type ([Figure 16](#), [Figure 17](#), [Figure 18](#) and [Figure 19](#)).

The ANCOVA analysis will be repeated on the mITT population using the subgroups defined in Section 6.4 for each test type (Table 27 and Table 28).

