11 STATISTICAL CONSIDERATIONS

11.1 Study Hypotheses

A formal hypothesis test is planned to compare nitazoxanide to placebo with respect to the primary efficacy outcome measure. The time from randomization until clinical resolution of Norovirus for at least 48 hours through 180 days will be compared between the two study arms.

The null hypothesis is that there is no difference in time until clinical resolution between study arms, with a two-sided alternative. The test for primary efficacy hypothesis will be conducted using a Log-Rank test at the 5% two-sided level of significance.

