2. INTRODUCTION

Gastroenteritis is defined as a self-limiting diarrheal illness that is often accompanied by nausea, vomiting, fever, or abdominal pain. In the United States, Norovirus is the single most common cause of acute gastroenteritis that leads to medical evaluation in adults, and the second most common cause of severe diarrhea in infants and young children [1, 2]. In the US, Norovirus is estimated to be responsible for 19 – 21 million episodes of gastroenteritis and 56,000 – 71,000 hospitalizations annually. [3] Increasingly, Norovirus is recognized as a common cause of chronic gastroenteritis in immunocompromised patients. Prolonged diarrhea can lead to dehydration, allograft dysfunction, renal insufficiency and rarely death in these patients [1, 4-9].

Noroviruses are small, non-enveloped, single-stranded RNA viruses that are members of the Caliciviridae. (1, 10] Of the five genogroups (GI – GV), GI, GII, and GIV are known to be human pathogens, although most are caused by GI and GII, which can be further classified into 30 unique genotypes. GII.4 has been recognized as the most common cause of outbreaks of Norovirus infections globally. [11, 12]

Norovirus is highly contagious as transmission is highly efficient with a median infectious dose of 18 viruses. There are generally high titers of virus within stool (10^5 to 10^{10} genome copies per gram of feces); [13, 14] therefore contact with infected feces and vomit, fecally-contaminated food, water and surfaces are common sources of infection. Norovirus is also highly stable with retained infectivity under environmental conditions that would generally inactivate other viruses, included chlorine at concentrations used in drinking water. [15, 16].

Norovirus infections typically present as an acute infection in immunocompetent hosts, with an incubation period of 10 to 51 hours. Symptoms include nausea, vomiting, watery non-bloody diarrhea, abdominal cramps and occasionally low-grade fever, muscle aches, chills and headache, [16] usually lasting from 20 to 60 hours. [17] While the acute phase of illness is typically short-lived, asymptomatic patients may continue to shed the virus for up to two weeks. [10, 16, 18] Unfortunately, approximately 570 – 800 deaths each year results from Norovirus infections in the US, with one third of fatal cases occurring in immunocompromised hosts. [19]

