4.5.1. Efficacy Variables

The primary efficacy variables to be assessed are the cessation of vomiting and no stools classified by the Bristol Stool Chart as diarrhea (Type 6 or 7) and are based on outcomes reported in the Subject Daily Diary. The subject diaries were prepared by Northwestern University. They will be reviewed and collected at every visit, including unscheduled or early termination visits. The Subject Daily Symptom Dairies will be completed by the subject daily, in real-time, from Day 1 through Day 180. All diaries should be completed at the same time every day, when possible. Subjects will complete the NNITS Daily Symptom Diary [Day 1 – 28] from the time of study treatment dispensation until visit 05. At visit 05 (Study Day 28), subjects will complete the NNITS Daily Symptom Diary – Post Treatment [Day 29 – 180].

The exploratory efficacy variables for the following outcome measures are also based on subject daily diaries:

- Time from randomization to initial clinical improvement in Norovirus disease through 28 and 180 days for at least 48 hours.
- Time from randomization to initial cessation of vomiting through Day 180 (recurrent vomiting will be considered disease recurrence unless determined to be due to another etiology [i.e. GVHD]).
- Time from randomization to subject report of no loss of appetite that is maintained for 48 hours through Day 180 (measure will be first time that the subject reports that they have no “loss of appetite” on their daily diary).
- Time from randomization to initial cessation of diarrhea through Day 180 classified by the Bristol Stool Chart as type 6 or 7 bowel movements (recurrent diarrhea will be considered disease recurrence unless determined to be due to another etiology [i.e. GVHD]).
- Time from randomization to 50% reduction in the amount of antimotility agents utilized by the subject through Day 180.
- Number of days of diarrhea through Days 28 and 180.
- Number of stools classified by the Bristol Stool Chart as type 6 or 7 bowel movements through Day 28.
- Number of days of IV hydration or total parenteral nutrition (TPN) therapy through Day 28.

The secondary efficacy variable to be assessed is viral load and is based on stool for Norovirus assays. Norovirus viral load assays will be performed in the [name] Laboratory (CCHMC, Cincinnati, OH) and will be measured using Quantitative RT-PCR (qRT-PCR) at Study Days 1, 7, 14, 21, 28, 60, 120, 180, and with recurrent diarrhea.

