5. SAMPLE SIZE CONSIDERATIONS

Sample size calculations assume a 50% reduction in the median duration of diarrhea for the nitazoxanide-treated group compared to those receiving placebo. The median diarrhea duration for the placebo group is assumed to be 135 days, while the median diarrhea duration for the treatment group is assumed to be 67.5 days. Given these assumptions, a sample size of 64 subjects in each arm (128 total) is required to achieve 90% power using the Log-Rank test. Accounting for a 20% attrition rate, final sample size will be 80 in each arm (160 total).

Though discouraged, the protocol allows for subjects in either study group to receive additional nitazoxanide after 28 days. Under the assumptions of treatment efficacy, additional treatment received by placebo subjects would reduce the median duration of symptoms for the placebo group to be closer to that of the nitazoxanide-treated group. It is assumed that subjects who would have the worst study outcomes (longest time to clinical resolution of diarrhea) will be the most likely to receive additional treatment. Subjects receiving additional treatment will be imputed as having the worst outcome (time to resolution censored at 180 days). Accounting for this imputation method, the power attained for the primary comparison was computed via simulation (R version 3.0.3). Estimated power is displayed in [Table 2](#), varying the proportion of subjects in each study group who receive additional treatment.

For example, if 15% of placebo subjects receive nitazoxanide, and 5-10% of subjects in the nitazoxanide-treated group receive additional treatment, the power is estimated to be 91.2%. Note that implausible scenarios (where substantially more nitazoxanide subjects receive additional treatment than do placebo subjects) have been omitted from the table.

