13. TECHNICAL DETAILS

SAS version 9.4 or above will be used to generate all tables, figures and listings or R version 4.1.1 or higher.

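### The Cox model for time to first negative viral load omits baseline viral load, although the companion ANCOVA in SAP 8.2 adjusts for it

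*SAP*

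**What the plan says.** - **Model (SAP 8.2).** The protocol's log-rank comparison (Protocol 11.4.3.2) is replaced by a stratified Cox model to "compare treatment to control through Day 180 with respect to time to first negative viral load". The only baseline factor is the acute/chronic stratum. A hazard ratio, 95% CI, likelihood-ratio p-value and medians are reported, separately for GII and GI. No tie method, covariate or interval-censored handling is named.
- **Sampling (SAP 4.5.1).** Viral load is measured "at Study Days 1, 7, 14, 21, 28, 60, 120, 180, and with recurrent diarrhea". That is seven scheduled post-baseline visits plus recurrence samples. SAP 4.1 allows ±3 days at Days 7 to 21, +3 at Day 28 and ±14 at Days 60, 120 and 180.
- **Event (SAP 3.3).** It falls on the first day with a negative or below-LLOQ result for the genogroup found at baseline. Subjects without a positive baseline result are excluded. Study day counts from randomization.
- **Companion endpoint (SAP 8.2).** The Day 1 to Day 180 change in titre is analysed by ANCOVA with baseline titre as covariate.
- **Software (SAP 13).** "SAS version 9.4 or above will be used to generate all tables, figures and listings or R version 4.1.1 or higher", so this clause does not settle the tie option.
- **Titre range (SAP 2).** The background text cites "generally high titers of virus within stool", 10^5 to 10^10 genome copies per gram.
- **Status (SAP 14.2).** Enrolment stopped at 31, and the analyses are described as mainly descriptive.

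**The concern.** Because the event is a threshold crossing, starting titre bears directly on the time needed to reach it. With about 15 subjects per arm, randomization cannot be relied on to balance it, and the model does nothing about a chance imbalance. The SAP accepts this reasoning for the change in titre but not for the time to negativity measured on the same samples.

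Two specification gaps sit beside it. Section 8.2 does not say whether events are dated by planned visit or by actual sample day, nor how ties are handled. It also takes a Kaplan-Meier median of detection dates, although clearance is known only to lie between two samples. At stake are the precision and reproducibility of one secondary hazard ratio and the meaning of its median.

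**Working it through.** **1. The plan's own power figure (primary endpoint only).** No power is stated for viral clearance. For the primary test the inputs are a level from Protocol 11.1 ("conducted using a Log-Rank test at the 5% two-sided level of significance") and two medians from SAP 5: "The median diarrhea duration for the placebo group is assumed to be 135 days" and "median diarrhea duration for the treatment group is assumed to be 67.5 days". With exponential times and 180 days of follow-up:
- event probabilities are 1 − 2^(−180/135) = 0.603 and 1 − 2^(−180/67.5) = 0.843, mean 0.723; HR = 2;
- Schoenfeld: 4(1.960 + 1.282)²/(ln 2)² ≈ 88 events, 61 per arm;
- Freedman: (1.960 + 1.282)² × 3² ≈ 95 events, 66 per arm.

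The stated figure, "a sample size of 64 subjects in each arm (128 total) is required to achieve 90% power using the Log-Rank test", lies between them, and 64/0.8 = 80 per arm. It is sound but says nothing about this secondary test. The two-sided 5% level is assumed to carry over.

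**2. Why baseline load matters.** Time to negativity is roughly (log10 baseline − log10 threshold) / rate of decline. The threshold is not in the documents; 10^4 is assumed. The assumed baseline is N(7.5, 1.25) in log10, limited to 5 to 10, to span the SAP 2 range. A subject at the mean must fall 3.5 log10. One SD higher, the fall is 4.75 log10, and 4.75/3.5 = 1.36 times as long at the same decline.

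**3. Chance imbalance.** The 95% limits for the between-arm difference, 15 against 16, are 1.96 × 1.25 × √(1/15 + 1/16) = ±0.88 log10. At the mean, (3.5 + 0.88)/3.5 = 1.25, which is not small beside an assumed drug effect of 1.6.

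**4. Simulation.** Inputs as above, plus control median 60 days, log-normal decline between subjects (SD 0.6), decline 1.6 times faster on drug, two strata, likelihood-ratio test. Actual days were drawn within the visit windows. Ranges cover repeat runs; Monte Carlo error on power is up to about 3 points.

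| Dating of events | Breslow | Efron | Efron + baseline load |
|---|---|---|---|
| Nominal visit day, power | 13–16% | 30–31% | 34–36% |
| Actual sample day, power | 32–34% | 33–34% | 42–46% |
| Actual sample day, null rejection | not compared | 5.5–7.2% | 7–9.8% |

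On actual days there were about 25 distinct event times, and the hazard ratios were close (Breslow 1.86, Efron 1.89). Run by run, the covariate moved power from 33% to 42%, 33% to 44% and 34% to 46%. Null rejection moved from 5.5% to 7%, 7% to 9% and 7.2% to 9.8%.

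**5. A different data model.** Proportional hazards, 31 subjects, placebo median 60 days, Efron ties on actual days; power without and with baseline load:

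| Baseline log-HR per SD | HR 2 | HR 3 |
|---|---|---|
| 0 | 35.7% → 35.0% | 74.0% → 72.0% |
| 0.5 | – | 63.3% → 71.3% |
| 1.0 | 22.7% → 33.2% | 46.2% → 65.7% |
| 1.5 | – | 26.2% → 56.8% |

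The gain runs from nothing to about 30 points with the prognostic strength, which the documents do not give. Null rejection at 1.0 per SD was 6.2% without and 6.3% with the covariate, so the inflation in step 4 is not universal.

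**6. The median.** Late gaps are 60 − 28 = 32, 120 − 60 = 60 and 180 − 120 = 60 days. With windows, the gap between the Day 60 and Day 120 samples can reach (120 + 14) − (60 − 14) = 88 days. A Kaplan-Meier median places clearance at the end of such a gap.

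**The case against.** - **No decision hangs on this power.** The trial stopped at 31, no power is claimed for the endpoint, and the analyses are mainly descriptive. This stands: power was 13–46% under every option in step 4. It limits the importance of the point, but section 8.2 still reports an HR, CI and p-value.
- **The gain is assumed and partly spurious.** The titre range is general background, not this trial's baseline, and the likelihood-ratio test became more liberal with the covariate in step 4. Both parts stand, so the gain is stated as approximate and the unadjusted model should be kept.
- **The analysed sample is below 31.** The GII/GI split and the exclusion of baseline-negative subjects shrink it further, making a covariate riskier. This stands and was not simulated.
- **The protocol test was unadjusted.** True, but the SAP has already replaced that test.
- **Keeping Cox for the HR while using an interval-censored median is inconsistent.** Only partly. In the step 5 model without a baseline effect, visit-only observation with Efron ties cost 3 to 7 points (77.0% to 74.2%; 41.5% to 34.8%), so Cox is serviceable for the HR. The median is where the visit gaps show directly.

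A reader might infer that sparse visits and an unnamed tie method roughly halve the power. That needs nominal-day dating with Breslow ties, and the documents point the other way. SAP 3.3 dates the event by the first day of a qualifying result, study day runs from randomization, the windows spread the dates, recurrence samples add more, and the clearance figures use days since randomization. Listing 17 carries both planned and actual days and Table 20 is laid out by visit, so the choice is not stated outright. Actual days are the likelier reading.

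**Conclusion.** The point holds in a limited form. The clearance model leaves out an already collected covariate that the same section uses elsewhere and that bears directly on a threshold-crossing event. Under the step 4 assumptions, including it raises power by about 10 points (about 32% to 42%), part of which is small-sample type I inflation (about 7% against 5.5%, and up to 9.8% against 7.2% in one run). If baseline load is not prognostic, there is no gain.

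Tie handling is a matter of specification, not a demonstrated loss: 16% against 30% on nominal days, 32% against 33% on actual days. No option turns this into a well-powered test. The documents do not support a claim that the plan as written halves its power.

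**What to change.** In SAP 8.2, for time to first negative viral load:
1. State that events and censoring are dated by actual sample day, and specify Efron ties in either package.
2. Add baseline log10 viral load as a covariate to the duration-stratified Cox model, within each genogroup. Keep the unadjusted model as a sensitivity analysis. Every analysed subject has a positive baseline result by SAP 3.3, so no new data are needed.
3. Report the median from an interval-censored (Turnbull) estimate with the visit interval in which it falls, and say how its 95% CI is obtained. The same paragraph calls this median a time to clinical resolution, whereas the Table 21 shell labels it time to first negative viral load; correct that too.
4. Fix these choices before treatment codes are used.

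A discrete-time complementary log-log model is not a better substitute at this size; its simulated type I error was 6–10%.

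The cost is a few sentences and one model option. The downsides are one degree of freedom, an HR conditional on baseline load, and a slightly liberal likelihood-ratio test, more of a risk in the smaller GI or GII sets. The report should carry that caveat beside the p-value.

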11.4.3.2 Analysis of Secondary Efficacy Outcome Measures

All secondary efficacy outcome measures will be assessed in the mITT and PP populations separately.

The secondary efficacy outcome measures are as follows:

1. The time from the randomization to first negative viral load through 180 days.
2. The change in viral titer between Day 1 and Day 180.

Secondary outcome measure 1 will be assessed through Kaplan-Meier curves along with results from a Log-Rank test to compare the time from randomization to first negative viral load between the nitazoxanide treated group and the placebo group.

Secondary outcome measure 2 will be assessed using analysis of covariance (ANCOVA) adjusting for baseline viral titer.

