The protocol calls for two-sample t-tests to be used for the below outcome measures. However, due to early closure of the study, the number of subjects is too small to meet the normality assumptions of the t-test; therefore Wilcoxon-Mann-Whitney exact rank sum tests will be used to compare treatment to placebo through Day 28 and/or Day 180 in the mITT analysis population (Table 30) for the following outcome measures (defined in Section 3.3):

- Number of days of diarrhea through Days 28 and 180.
- Number of stools classified by the Bristol Stool Chart as type 6 or 7 bowel movements through Day 28.
- Number of days of IV hydration or total parenteral nutrition (TPN) therapy through Day 28.

The following patient-reported outcome measures will be assessed using ANCOVA adjusting for the baseline patient-reported measure:

- Change in patient-reported quality of life as measured by EuroQOL-5 (global) and IBSQOL (diarrhea specific) [adult] or Euro QOL-5 Peds (global) and PedsQL GI Module [children] from baseline to Day 180.
- Change in patient-reported physical function as measured by the NIH PROMIS Physical Function (Adult) Pediatric Global Health (Peds) from baseline to Day 180.
- Change in patient-reported emotional distress as measured by the NIH PROMIS Depression, Anxiety, Fatigue (Adult and Peds) from baseline to Day 180.
- Change in patient-reported gastrointestinal symptoms as measured by the NIH PROMIS GI (Adult and Peds) symptoms (6 of 8 subscales) from baseline to Day 180.

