Note: HR is the ratio of the hazard of first negative GII viral load in each treatment group estimated from the Cox model. The ratio is Nitazoxanide to Placebo.

HR for the ‘Any Duration’ group is the hazard ratio from the stratified Cox Model.

P-value calculated using the likelihood ratio test.

Table with similar format:

Table 24: Time to First Negative Viral Load by Treatment Group and Duration of Symptoms: Subgroup Sensitivity Analysis – Norovirus GI, mITT Population

Table 25: Change in Viral Titer between Day 1 and Day 180 by Treatment Group and Duration of Symptoms – Norovirus GII

[Implementation Note: If a transformation of the dependent variable is used, a footnote in the table will denote which transformation was used in the analyses. If the assumptions of ANCOVA cannot be met, only the observed mean, standard deviation and 95% confidence intervals of the unadjusted change in viral titer between Day 1 and Day 180 will be reported. If an estimate is not calculable, insert “NC” in the cell and add a footnote “NC = Not calculable.” If a subgroup has less than 5 subjects per treatment group, then remove rows and add footnote specifying which group(s) are excluded from analyses.]

Analysis Population	Treatment Group	Duration of Symptoms	n	Observed Mean	Standard Deviation	Adjusted Mean	Standard Error	95% CI	P-value
mITT Population	Nitazoxanide 500 mg (N=X)	Acute (Baseline Mean = xx.x)	x	x.x	x.x	x.x	x.x	x.x, x.x	---
	Placebo (N=X)		x	x.x	x.x	x.x	x.x	x.x, x.x	
	Nitazoxanide 500 mg (N=X)	Chronic (Baseline Mean = xx.x)	x	x.x	x.x	x.x	x.x	x.x, x.x	---
	Placebo (N=X)		x	x.x	x.x	x.x	x.x	x.x, x.x	
	Nitazoxanide 500 mg (N=X)	Any Duration (Baseline Mean = xx.x)	x	x.x	x.x	x.x	x.x	x.x, x.x	0.xxx
	Placebo (N=X)		x	x.x	x.x	x.x	x.x	x.x, x.x	

Implementation note: Repeat for the Per Protocol Population.

N = Number of subjects in the specified treatment group, duration of symptoms strata, and analysis population with positive GII test results at baseline.

n = Number of subjects with Norovirus GII results at Day 1 and Day 180.

Note: Adjustments based on Baseline Viral Titer.

P-value is the test of between-treatment differences for change in viral titer from Day 1 to Day 180.

Table with similar format:

Table 26: Change in Viral Titer between Day 1 and Day 180 by Treatment Group and Duration of Symptoms – Norovirus GI

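### SAP 8.2 fixes no scale for the ANCOVA of change in viral titer, so whether a treatment test is reported, and on what scale, is settled after the data are seen

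*SAP*

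**What the plan says.** Protocol 11.4.3.2 gives the model in one sentence: "Secondary outcome measure 2 will be assessed using analysis of covariance (ANCOVA) adjusting for baseline viral titer". SAP 8.2 keeps it, for GII and GI separately: the change "will be assessed using analysis of covariance (ANCOVA) adjusting for baseline viral titer". Neither says whether copies or log copies are analysed. The Table 25 shell adds only "Adjustments based on Baseline Viral Titer" and the count rule "n = Number of subjects with Norovirus GII results at Day 1 and Day 180", with no units.

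Two nearby statements do not supply a scale. SAP 3.3 takes the geometric mean of assay replicates within a specimen. Table 20 shows geometric mean titers by arm, but as a separate descriptive display.

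SAP 8.2 then sets a sequence:

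1. Levene's test and normality checks are run. No normality test or cut-off is named.
2. If they pass, adjusted means, confidence intervals and a p-value are shown.
3. If they fail, "transformations of the change in viral titer variable may be utilized to correct any skewness in residuals or heterogeneity of the variances", disclosed by a table footnote.
4. If that fails too, the report contains "only the observed mean, standard deviation and 95% confidence intervals of the unadjusted change in viral titer".

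The section closes without any condition: "A forest plot will display the adjusted means and 95% confidence intervals of the change in viral titer between Day 1 and Day 180" (Figures 16-19).

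**The concern.** Titers spread over about five orders of magnitude are poorly suited to an additive model in copies. If the untransformed analysis is the default, it will seldom pass the SAP's own checks, and what is reported then turns on a transformation that is optional, unnamed and unordered. SAP 8.2 does not require the choice to be made blind to treatment arm, and Levene's test across arms needs the arms.

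Three things follow. A named secondary efficacy endpoint may end with no between-arm test. Where a test does appear, the choice among passing transformations can decide significance. And the forest plots of adjusted means have nothing to show if step 4 is reached. Elsewhere in the same small sample the SAP avoided the first outcome: for day and stool counts, SAP 8.3 says "the number of subjects is too small to meet the normality assumptions of the t-test; therefore Wilcoxon-Mann-Whitney exact rank sum tests will be used".

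**Working it through.** **No plan figure to reproduce.** The documents state no SD, effect or power for this endpoint. The check is an illustration of the scale followed by simulation.

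**Why the scale matters.** Take LLOQ = 10^3 (assumed), so a negative is imputed at 500 under the half-LLOQ rule in SAP 3.3.
- Subject A falls from 10^10 to 10^9: change in copies -9×10^9; change in log10 -1.
- Subject B falls from 10^6 to negative: change in copies 500 - 10^6 = -999,500; change in log10 2.70 - 6 = -3.30.

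In copies, A's change is about 9,000 times B's (9×10^9 / 999,500), although B cleared the virus and A did not.

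**Models compared.** V1 and V180 are the Day 1 and Day 180 titers.
- SAP route: f(V180 - V1) = a + b·V1 + c·arm + error, reported only if the residuals pass both checks. The first passing f is used.
- Alternative: log10 V180 - log10 V1 = a + b·log10 V1 + c·arm + error, always reported. The ratio of fold changes is 10^c.

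The SAP transforms only the change, and most changes are negative (92-97% in the second simulation below), so a plain log of the change is undefined for most subjects.

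**Inputs.** From the documents: 31 enrolled; paired Day 1 and Day 180 results required; negatives at half LLOQ; values above ULOQ set to ULOQ. Assumed: baseline log10 mean 7.5, SD 1.3; LLOQ 10^3; uncleared subjects fall 1 log10 (SD 1.3); ULOQ none, 10^9 or 10^8; Shapiro-Wilk and median-centred Levene at 5%. Short list of f, in order: raw, cube root, signed log, shifted log. The broad list adds signed square root, reflected log, Yeo-Johnson and log ratio. There were 1000 trials per cell.

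**Results** (ranges over the assumed scenarios):

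| | n = 31 | n = 24 | n = 16 |
|---|---|---|---|
| Raw copies pass both checks | 0-12% | 0-19% | 2-35% |
| No test reached, broad list | 18-67% | 11-45% | 4-20% |
| No test reached, short list | 62-90% | 51-76% | 30-40% |
| No test reached, broad list, checks at 1% | 6-35% | 4-17% | 0.5-6% |
| Log10 model passes both checks | 6-72% | 15-78% | 31-82% |

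Chance of a reported p<0.05, SAP route (broad list) against log10 always reported:

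| Negative at Day 180 | n = 31 | n = 24 | n = 16 |
|---|---|---|---|
| 40% v 90% | 19-33 v 78-80% | 20-24 v 65-68% | 13-14 v 47-51% |
| 50% v 80% | 11-17 v 35-38% | 10-13 v 29% | 7-9 v 17-23% |
| 20% v 40% | 12 v 18-20% | 9-10 v 14-15% | 6-9 v 11% |

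**Order of trying.** Taking the smallest passing p-value, at 40% v 90%, still gives only 25-46 / 30-39 / 29-34% for n = 31 / 24 / 16. Where two or more candidates pass and there is a true effect, they disagree on p<0.05 in 14-54% of trials.

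**Type I error.** With no effect, log10 rejects in 4.5-6.4% and rank ANCOVA in 3.9-6.3%. Among null trials that report a test, picking the smallest passing p rejects in 8-13%.

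**Sensitivity** (n = 24, 40% v 90%; baseline SD 0.8 or 1.3, fall 0 or 2 log10, LLOQ 10^3 or 10^4, ULOQ none or 10^8). No test is reached in 7-54% (broad) or 26-88% (short); reported p<0.05 is 9-32% against 53-74% for log10.

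**Second simulation, different inputs** (16 + 15 subjects, fall 1.5 log10, SD 1.25, 3000 trials per scenario). Raw change passes in about 0%. With no effect, at least one of five scales gives p<0.05 in 11-12% of trials. At 70% v 40% negative, p<0.05 occurs in 29% on log10 against 2% raw, 5% cube root, 3% asinh and 5% for ranks of the change.

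**The case against.** - **A default is implied.** Transformation is considered only after the checks fail, so untransformed titer comes first, and the trigger is residual behaviour rather than the p-value. This is a fair reading, but that default rarely passes and everything after it is open.
- **The covariate's scale is not stated.** The simulated SAP route uses raw baseline. With log10 baseline and the same eight candidates at n = 31, the no-test rate moves from 25% to 78% (50% v 80%, no ULOQ) and from 51% to 30% (20% v 40%, ULOQ 10^8). The no-test figures are therefore soft. The main contrast survives: at 40% v 90%, log10 always reported reaches 77-80% against 14-18%.
- **The magnitude has no anchor in the documents.** The no-test range runs from 0.5% to 90%, and the normality checks could be graphical. This stands: the simulation shows a material possibility, not a forecast.
- **31 is a ceiling.** Baseline negatives are excluded, genogroups are analysed apart, both visits are needed, and subgroups with fewer than five per arm are dropped from efficacy displays (SAP 8). At n = 16 the broad-list no-test rate is only 4-20%.
- **The rank-test comparison is selective.** The SAP's other baseline-adjusted changes, patient-reported outcomes (8.3) and immunoglobulins (10), follow the same check, transform and describe sequence. True, but that shows the weakness is shared.
- **Impact is limited.** SAP 14.2 calls the analyses primarily descriptive, and the Cox model for time to first negative keeps its hazard ratio and p-value. This bears on priority. Table 25 still promises a p-value for this endpoint, and footnoting a transformation is disclosure, not pre-specification.

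**Conclusion.** The concern holds. No scale is named in the protocol, SAP 8.2 or the table shell, and the route to a p-value runs through undefined checks and an undefined transformation to a fallback without a test. The unconditional forest plots conflict with that fallback.

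The size is conditional on the assumed inputs. The chance of no test falls as paired subjects become fewer and rises if few transformations are tried. The loss of power is large when clearance differs strongly between arms (40% v 90%) and under 10 points at 20% v 40%. It should be fixed, with medium confidence in the size: it affects the interpretability of one secondary endpoint in a trial closed at 31 subjects, not the primary conclusion.

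**What to change.** In SAP 8.2:

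1. Define the outcome as log10(Day 180) minus log10(Day 1), with log10 baseline as covariate and assay limits handled as in SAP 3.3.
2. State the value for detected results below LLOQ. SAP 3.3 counts them as undetectable but gives an imputed value only for negatives.
3. Report the ratio of adjusted geometric mean fold changes with 95% CI and p-value whatever the Levene and normality checks show. Naming log10 but keeping the gate is not enough, because the half-LLOQ floor often makes log10 fail too. Figures 16-19 can then always be drawn.
4. Replace the transform-the-change step with one pre-specified rank ANCOVA or censored-data sensitivity analysis, and say exactly what is ranked. In the main simulation rank ANCOVA had power of 77-79 / 65 / 45-47% at 40% v 90% (n = 31 / 24 / 16), whereas ranking the raw change against raw baseline did little in the second simulation (5% against 29%).

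The cost is SAP wording and a few lines of code, with no new data. The effect is read as a fold change, in line with Table 20, and partly reflects the imputed value when many subjects are negative; the sensitivity analysis addresses that. Log10 does not cure the small sample: at 50% v 80% negative, power is 35-38% at n = 31 and 17-23% at n = 16.
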